## 7.1. Time and Events Tables

### 7.1.1. Group A

Procedure	Screening (up to Day - 28)	Day -15	Day -14	Day - 13 to - 1	Day 1	Day 2 to Day 13	Day 14	Day 15 to Day 20	Day 21 to Day 27	Day 28	Day 29 to 42	Follow- up a	a All procedures listed to also be conducted if a subject decides to prematurely withdraw/discontinue
Informed Consent	X												
Inc/Exc criteria assessment	X												
Demography	X												
Pregnancy Test (women)	X				X		X					X	Pregnancy testing to be performed at Screening, on Day 1 (pre-dose), Day 14 (pre-dose) and once during follow-up, with day recorded
TSH, free T4, free T3	X				X		X					X	
Vital Signs	X	X			X		X			X			
Safety Lab Samples (clin chem, haematol, Urinalysis)	X	X		X	X		X			X		X	On days of dosing samples should be taken predose.  Sample timepoints during the Day-13 to Day-1 period are as follows: – once weekly during visits to assess PV lesion development
Full Physical Exam	X											X	

Procedure	Screening (up to Day - 28)	Day -15	Day -14	Day - 13 to - 1	Day 1	Day 2 to Day 13	Day 14	Day 15 to Day 20	Day 21 to Day 27	Day 28	Day 29 to 42	Follow- up a	a All procedures listed to also be conducted if a subject decides to prematurely withdraw/discontinue
Brief Physical Exam				X									Assessment to be performed pre-dose  Sample timepoints during the Day-13 to Day-1 period are as follows: – once weekly during visits to assess PV lesion development
12-lead ECG	X				X		X					X	On days of dosing assessments should be performed pre-dose
SLE clinical assessment	X				X					X		X	On days of dosing assessment as defined by the investigator to be performed pre-dose .
ANA, anti-dsDNA, anti-Ro and anti-La antibodies, HIV, Hep B, Hep C, FSH, Drug screen	X												
Skin Biopsies					X b					X b			b Day 1 biopsies will be taken pre-dose. Day 28 biopsies will be taken 4 hours post-dose
UV threshold testing		X											
Photoprovocation				X c, d									Performed 24 hours after UV threshold testing. c PV occurs once every 24 hours for 3 days on Day-14, Day-13 & Day-12. d If PV induced lesions appear at all 3 sites after Day -14 or Day -13, PV treatment can be stopped early

Procedure	Screening (up to Day - 28)	Day -15	Day -14	Day - 13 to - 1	Day 1	Day 2 to Day 13	Day 14	Day 15 to Day 20	Day 21 to Day 27	Day 28	Day 29 to 42	Follow- up a	a All procedures listed to also be conducted if a subject decides to prematurely withdraw/discontinue
Lesion induction assessment			<----X---->										
Lesion resolution assessment											X	X	
Clinical score				X		X				X			Components of the RCLASI as defined in Section 7.3 Assessments to be performed pre-dose
Local Tolerability Assessment				X	X	X	X	X	X	X			Assessments to be performed pre-dose and up to one hour following dosing on days of dosing
Dosing				X	X	X	X	X	X	X			Once daily
Randomisation				X									Pre-dose

Procedure	Screening (up to Day - 28)	Day -15	Day -14	Day - 13 to - 1	Day 1	Day 2 to Day 13	Day 14	Day 15 to Day 20	Day 21 to Day 27	Day 28	Day 29 to 42	Follow- up a	a All procedures listed to also be conducted if a subject decides to prematurely withdraw/discontinue
PK blood sample					X	X	X		X	X	X	X	Sampling timepoints: Day 1 = pre-dose; and 5hrs ( $\pm 1$ hr)  Between Day 2 and Day13: one pre-dose sample or postdose sample with time recorded since last dose  Day 14: predose sample  Between Day 21 and Day27: one pre-dose sample or postdose sample with time recorded since last dose  Day 28: one postdose sample with time recorded since last dose  Between Day 29 and Day 42: one sample with time recorded since last dose  Follow-up visit: one sample with sampling day recorded
AE/SAE Review	X								X				
Concomitant Medication Review	X								X				

### 7.1.2. Group A PV non-responders

Procedure	Once-weekly up to 28 days after first photoprovocation	Final Follow-up visit(s) (occurs until final PV induced lesion has resolved)	Notes
Brief Physical Exam	X	X	IMPORTANT: This table is ONLY applicable for subjects in group A that do not develop PV induced lesions within 14 days of the start of photoprovocation. Once-weekly assessments will occur from 15 days post first photoprovocation up until 28 days post first photoprovocation. Any PV lesion that develops after 15 days post-photoprovocation will be followed up until resolution.
PV Lesion assessment (if present)	X	X	
AE/SAE Review	X	X	
Concomitant Medication Review	X		

## 7.1.3. Group B

Procedure	Screening (up to Day -28)	Day -5 to -3	Day 1	Day 2 to Day 13	Day 14	Day 15 to Day 20	Day 21 to Day 27	Day 28	Day 29 to 42	Follow-up (between Day 43 to Day 56) a	All procedures listed to also be conducted if a subject decides to prematurely withdraw/discontinue
Informed Consent	X										
Inc/Exc criteria assessment	X										
Demography	X										
Pregnancy Test (women)	X		X		X				X	Pregnancy testing to be performed at Screening, on Day 1 (pre-dose), Day 14 (pre-dose) and once during follow-up, with day recorded	
TSH, free T4, freeT3	X		X		X				X		
Vital Signs	X	X			X			X			
Safety Lab Samples (clin chem ,haematol, Urinalysis)	X	X	X		X			X	X	On days of dosing samples should be taken predose	
Full Physical Exam	X								X		
Brief Physical Exam			X							Assessment to be performed pre-dose	
12-lead ECG	X		X		X				X	On days of dosing assessments should be performed predose	
SLE clinical assessment	X		X					X	X	On days of dosing assessment as defined by the investigator to be performed pre-dose .	
ANA, anti-dsDNA antibodies, anti-Ro and anti-La antibodies, HIV, Hep B, Hep C, FSH, Drug screen	X										
Lesion selection		X								Refer to Section 4.1 and	

Procedure	Screening (up to Day -28)	Day -5 to -3	Day 1	Day 2 to Day 13	Day 14	Day 15 to Day 20	Day 21 to Day 27	Day 28	Day 29 to 42	Follow-up (between Day 43 to Day 56) a	a All procedures listed to also be conducted if a subject decides to prematurely withdraw/discontinue
											Section 6.1
Skin Biopsies		X b						X b			b 2 to 4 days healing time will be allowed prior to randomisation and the first dose. Day 28 biopsies will be taken 4 hours post-dose
Clinical score			X		X			X			
Local tolerability Assessment			X	X	X	X	X	X	X		Assessments to be performed pre-dose and up to one hour following dosing on days of dosing
Dosing			X	X	X	X	X	X			Once daily
Randomisation			X								Pre-dose

Procedure	Screening (up to Day -28)	Day -5 to -3	Day 1	Day 2 to Day 13	Day 14	Day 15 to Day 20	Day 21 to Day 27	Day 28	Day 29 to 42	Follow-up (between Day 43 to Day 56) a	a All procedures listed to also be conducted if a subject decides to prematurely withdraw/discontinue
PK blood sample			X	X	X		X	X	X	X	
Sampling timepoints: Day 1 = pre-dose; and 5hrs (<math>\pm 1</math> hr)
 
Between Day 2 and Day13: one pre-dose sample or postdose sample with time recorded since last dose
 
Day 14: predose sample
 
Between Day 21 and Day27: one pre-dose sample or postdose sample with time recorded since last dose
 
Day 28:one postdose sample with time recorded since last dose
 
Between Day 29 and Day 42: one sample with time recorded since last dose
 
Follow-up visit: one sample with sampling day recorded

AE/SAE Review						X					
Concomitant Medication Review						X					
Lesion resolution assessment								X	X		

## 7.2. Screening and Critical Baseline Assessments

Cardiovascular medical history/risk factors (as detailed in the CRF) will be assessed at screening.

The SLE clinical assessment is an assessment defined by the investigator as per usual practice at their site and is used to determine predominant skin disease and no evidence of life or organ threatening systemic features.

The following demographic parameters will be captured: year of birth, sex, race and ethnicity. In addition, smoking & alcohol history will be recorded.

Procedures conducted as part of the subject's routine clinical treatment and obtained prior to signing of informed consent may be utilized for screening or baseline purposes provided the procedure meets the protocol-defined criteria and has been performed in the timeframe of the study.

## 7.3. RCLASI (Clinical Score)

The RCLASI (Revised Cutaneous Lupus Erythematosus Disease Area and Severity Index) will be used to assess disease activity. RCLASI has been previously described by [Kuhn, 2010] as reliable in a multi-centre clinical trial setting for evaluation of CLE disease activity and damage to the skin in CLE sub-types.

In this study, components of the RCLASI will be utilised: only activity and dyspigmentation part of the damage scores will be recorded for lesions. All other sections in the RCLASI (site of involvement, mucous membrane lesions, and alopecia will not be used for clinical activity score).

**Figure 2 RCLASI sub-section**

CCI - This section contained Clinical Outcome Assessment data collection questionnaires or indices, which are protected by third party copyright laws and therefore have been excluded.

## **7.4. Safety**

Planned time points for all safety assessments are listed in the Time and Events Table (Section 7.1). Additional time points for safety tests [(such as vital signs, physical exams and laboratory safety tests)] may be added during the course of the study based on newly available data to ensure appropriate safety monitoring.

### **7.4.1. Adverse Events (AE) and Serious Adverse Events (SAEs)**

The definitions of an AE or SAE can be found in Section 12.3.

The investigator and their designees are responsible for detecting, documenting and reporting events that meet the definition of an AE or SAE.

#### **7.4.1.1. Time period and Frequency for collecting AE and SAE information**

- Any SAEs assessed as related to study participation (e.g., protocol-mandated procedures, invasive tests, or change in existing therapy) or related to a GSK product will be recorded from the time a subject consents to participate in the study up to and including any follow-up contact.

- AEs will be collected from the start of Study Treatment until the follow-up contact (see Section 7.4.1.3), at the timepoints specified in the Time and Events Table (Section 7.1).
- Medical occurrences that begin prior to the start of study treatment but after obtaining informed consent may be recorded on the Medical History/Current Medical Conditions section of the CRF.
- All SAEs will be recorded and reported to GSK within 24 hours, as indicated in Section 12.3 Appendix 3.
- Investigators are not obligated to actively seek AEs or SAEs in former study subjects. However, if the investigator learns of any SAE, including a death, at any time after a subject has been discharged from the study, and he/she considers the event reasonably related to the study treatment or study participation, the investigator must promptly notify GSK.

NOTE: The method of recording, evaluating and assessing causality of AEs and SAEs plus procedures for completing and transmitting SAE reports to GSK are provided in [Appendix 4](#).

#### **7.4.1.2. Method of Detecting AEs and SAEs**

Care will be taken not to introduce bias when detecting AEs and/or SAEs. Open-ended and non-leading verbal questioning of the subject is the preferred method to inquire about AE occurrence. Appropriate questions include:

- “How are you feeling?”
- “Have you had any (other) medical problems since your last visit/contact?”
- “Have you taken any new medicines, other than those provided in this study, since your last visit/contact?”

#### **7.4.1.3. Follow-up of AEs and SAEs**

After the initial AE/SAE report, the investigator is required to proactively follow each subject at subsequent visits/contacts. All SAEs, and non-serious AEs of special interest (as defined in Section 12.3) will be followed until resolution, until the condition stabilizes, until the event is otherwise explained, or until the subject is lost to follow-up (as defined in Section 5.4). Further information on follow-up procedures is given in [Appendix 3](#).

#### **7.4.1.4. Cardiovascular and Death Events**

For any cardiovascular events detailed in Section 12.3.3 and all deaths, whether or not they are considered SAEs, specific Cardiovascular (CV) and Death sections of the CRF will be required to be completed. These sections include questions regarding cardiovascular (including sudden cardiac death) and non-cardiovascular death.

The CV CRFs are presented as queries in response to reporting of certain CV MedDRA terms. The CV information should be recorded in the specific cardiovascular section of the CRF within one week of receipt of a CV Event data query prompting its completion.

#### **7.4.1.5. Disease-Related Events and/or Disease-Related Outcomes Not Qualifying as SAEs**

The following disease related events (DREs) are common in subjects with CLE or SLE and can be serious/life threatening:

- Exacerbation of SLE or transformation of CLE into SLE with organ involvement other than the skin

Because these events are typically associated with the disease under study, they will not be reported according to the standard process for expedited reporting of SAEs to GSK (even though the event may meet the definition of a SAE). These events will be recorded on the DRE page in the subject's CRF within the appropriate time frame *agreed upon by the SRT* for completion of DRE CRF pages. These DREs will be monitored by the SRT (see Section 10.8) on a routine basis.

*NOTE: However, if either of the following conditions apply, then the event must be recorded and reported as an SAE (instead of a DRE):*

- *The event is, in the investigator's opinion, of greater intensity, frequency, or duration than expected for the individual subject, or*
- *The investigator considers that there is a reasonable possibility that the event was related to treatment with the investigational product*

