## 5.2. Exclusion Criteria

A subject will not be eligible for inclusion in this study if any of the following criteria apply:

CONCURRENT CONDITIONS/MEDICAL HISTORY (INCLUDES LIVER FUNCTION AND QTC INTERVAL)

1. ALT >2xULN;
 
2. Bilirubin >1.5xULN (isolated bilirubin >1.5xULN is acceptable if bilirubin is fractionated and direct bilirubin <35%)
 
3. Current or chronic history of liver disease, or known hepatic or biliary abnormalities (with the exception of Gilbert's syndrome or asymptomatic gallstones)
 
4. QTcF > 450 msec, or QTcF > 480 msec in subjects with Bundle Branch Block
 
NOTES:
 
 
• The QTc is the QT interval corrected for heart rate according to Bazett's formula (QTcB), Fridericia's formula (QTcF), and/or another method, machine-read or manually over-read.
 
• The specific formula that will be used to determine eligibility and discontinuation for an individual subject should be determined prior to initiation of the study. In other words, several different formulae cannot be used to calculate the QTc for an individual subject and then the lowest QTc value used to include or discontinue the subject from the trial.
 
• For purposes of data analysis, QTcB, QTcF, another QT correction formula, or a composite of available values of QTc will be used as specified in the Reporting and Analysis Plan (RAP).
 
 
5. History of any past or present benign or malignant skin conditions and disease, unless in the opinion of the investigator it will not compromise the subjects safety and quality of data.
 
6. Subjects with active Systemic Lupus Erythematosus (SLE) and/or significant disease in any other organ than the skin, as judged by the Investigator after discussion with the medical monitor
 
7. Subjects with a history of Graves disease
 
8. Subjects with a history of thyroid cancer.
 
9. Unable to refrain from vitamins, herbal and dietary supplements (including St John's Wort) within 7 days (or 14 days if the drug is a potential enzyme inducer) or 5 half lives (whichever is longer) prior to the screening visit until the completion of the follow-up assessments, unless in the opinion of the Investigator, in consultation with the GSK Medical Monitor if required, the medication will not interfere with the study procedures or compromise subject safety.
 
10. Clinically significant abnormality in the hematological, clinical chemistry, or urinalysis screen, that in the opinion of the investigator after discussion with the

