7. PRIMARY STATISTICAL ANALYSES

7.1. Safety Analyses

7.1.1. Overview of Planned Adverse Events Analyses

The safety analyses will be based on the Safety population, unless otherwise specified.

Table 3 provides an overview of the planned analyses, with full details of data displays being presented in [Appendix 8: List of Data Displays](#).

Table 3 Overview of Planned Adverse Events Analyses

Endpoint / Parameter/ Display Type	Absolute		
	Summary		Individual
	T	F	L
Adverse Events (AEs)			
All AEs by SOC	Y		Y
All Drug-Related AEs by SOC	Y		
Subject Numbers for Individual AEs			Y
Relationship Between AE SOCs, PT & Verbatim Text			Y
Serious and Other Significant AEs			
Non-Fatal Serious AEs			Y
Serious AEs by SOC	Y		
Reasons for Considering as a Serious AE			Y
AEs Leading to Withdrawal from Study / Permanent Discontinuation of Study Treatment by Overall Frequency	Y		Y

[1] Plot of common AEs and relative risk will be generated.

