11.8.5. Safety Tables

Safety : Tables					
No.	Population	IDSL / TST ID / Example Shell	Title	Programming Notes	Deliverable [Priority]
Adverse Events					
2.1.	Safety	CP_AE1p	Summary of All Adverse Events by System Organ Class (Group B-Natural Lesions)	Only Total adverse events will be summarised.	SAC
2.2.	Safety	CP_AE1p	Summary All Drug-Related Adverse Events by System Organ Class (Group B-Natural Lesions)	Only Total adverse events will be summarised.	SAC

Safety : Tables					
No.	Population	IDSL / TST ID / Example Shell	Title	Programming Notes	Deliverable [Priority]
Serious and Other Significant Adverse Events					
2.3.	Safety	CP_AE1p	Summary of Serious Adverse Events by System Organ Class (Group B-Natural Lesions)	Only Total adverse events will be summarised.	SAC
2.4.	Safety	CP_AE1p	Summary of Adverse Events Leading to Withdrawal from Study / Permanent Discontinuation of Study Treatment by Overall Frequency (Group B-Natural Lesions)	Only Total adverse events will be summarised.	SAC
Laboratory: Chemistry					
2.5.	Safety	LB1	Summary of Chemistry Changes from Baseline (Group B-Natural Lesions)	Treatment column will not be displayed.	SAC
2.6.	Safety	LB3	Summary of Emergent Chemistry Results Relative to Normal Range (Group B-Natural Lesions)	Treatment columns will be replaced by one 'Part B' column	SAC
Laboratory: Hematology					
2.7.	Safety	LB1	Summary of Hematology Changes from Baseline (Group B-Natural Lesions)	Includes baseline values. Treatment column will not be displayed.	SAC
2.8.	Safety	LB3	Summary of Emergent Hematology Results Relative to Normal Range (Group B-Natural Lesions)	As notes for Chemistry T2.12.	SAC
Laboratory: Urinalysis					
2.9.	Safety	LB1	Summary of Urine Concentration Changes from Baseline (Group B-Natural Lesions)	Includes Baseline values. Treatment column will not be displayed.	SAC
2.10.	Safety	LB2	Summary of Emergent Urinalysis Dipstick Results (Group B-Natural Lesions)	As above for Chemistry, using dipstick categories.	SAC
Laboratory: Hepatobiliary (Liver)					
2.11.	Safety	LIVER1	Summary of Liver Monitoring/Stopping Event Reporting (Group B-Natural Lesions)	Treatment columns will be replaced by one 'Part B' column	SAC

Safety : Tables					
No.	Population	IDSL / TST ID / Example Shell	Title	Programming Notes	Deliverable [Priority]
2.12.	Safety	LIVER10	Summary of Subjects Meeting Emergent Hepatobiliary Laboratory Abnormality Criteria (Group B-Natural Lesions)	Treatment columns will be replaced by one 'Part B' column	SAC

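### The SAP has no display for disease-related events, so a serious systemic lupus event judged expected and unrelated would be left out of the SAE counts and listings

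*Protocol*

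**What the plan says.** Protocol 7.4.1.5 names one class of disease-related event: "Exacerbation of SLE or transformation of CLE into SLE with organ involvement other than the skin". It accepts that such events can be serious or life-threatening, and says that "they will not be reported according to the standard process for expedited reporting of SAEs to GSK", even where the SAE definition is met. On recording it says: "These events will be recorded on the DRE page in the" subject's CRF.

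A note in the same section limits this. If the event is more intense, more frequent or longer than expected in that patient, or if the investigator sees a reasonable possibility that the product caused it, "then the event must be recorded and reported as an SAE (instead of a DRE". The section also provides oversight during the study: "These DREs will be monitored by the SRT" routinely.

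SAP 7.1.1 (Table 3) sets out the serious-event displays in terms of AEs and SAEs only, with rows such as "Reasons for Considering as a Serious AE". In SAP 11.8.5, Table 2.3 is titled "Summary of Serious Adverse Events by System Organ Class (Group B-Natural Lesions". SAP 11.8.1 numbers the safety tables 2.1 to 2.20 and the listings 1 to 44. None is for DREs. The abbreviation list has no entry for the term, and SAP 2.1, which records departures from the protocol's analysis, does not say that DREs were dropped.

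**The concern.** The primary objective is safety and tolerability, assessed partly through AE reporting. The protocol creates a third route for one kind of event, next to AE and SAE, and gives it its own CRF page. The SAP's displays follow only the AE and SAE routes. Data collected on the third route have no planned destination in the report.

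The events concerned are ones the protocol itself calls potentially life-threatening. Whether such an event counts as an SAE or a DRE depends on the investigator's view of expectedness and causality. If the report shows only the events that came back to SAE status, its reader cannot see how many went the other way or whether the judgement was reasonable. In a trial of about 20 randomised subjects, one event is enough to change the serious-event count from none to one.

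**Working it through.** Whether the gap exists is settled by reading. The arithmetic only shows its size.

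**Step 1: where a serious DRE is recorded.** Protocol 7.4.1.5 waives expedited reporting, and its note treats SAE and DRE as alternatives. Appendix 3 points the same way. Section 12.3.1 excludes expected progression of the disease under study from the AE definition, unless it is more severe than expected. Section 12.3.2 adds that something which is not an AE cannot be an SAE, whatever its seriousness. The outcomes are:

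| Investigator's judgement | Recorded as | SAP output |
|---|---|---|
| Worse than expected for the patient | SAE | Table 2.3, Listings 18-19 |
| Possibly related to the product | SAE | Table 2.3, Listings 18-19 |
| Expected and unrelated | DRE page | None |

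The gap is the third row.

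**Step 2: the SAP displays.**
- Tables 2.1-2.4: AEs, drug-related AEs, SAEs, and AEs leading to withdrawal or discontinuation.
- Tables 2.5-2.20: laboratory, liver, ECG, vital signs and local tolerability.
- Listings 14-20: AEs and SAEs. Listing 15 covers AEs in photoprovocation (PV) failures.
- Listings 21-33 and 35: liver, laboratory, ECG, vital signs and local tolerability.
- The remaining listings: study population, RCLASI, pharmacokinetics and biomarkers.

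No item takes its data from the DRE page.

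**Step 3: the protocol's own precision figures.** Protocol 9.2.1 uses a flat Beta(1,1) prior, so x events in n subjects give a Beta(1 + x, 1 + n − x) posterior.
- 1/15: Beta(2, 15), 2.5% and 97.5% points 0.016 and 0.302. The protocol states 0.02 to 0.30; reproduced.
- 0/15: Beta(1, 16), 97.5% point 1 − 0.025^(1/16) = 0.206. The protocol states 21%; reproduced.

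**Step 4: the effect of one undisplayed event.** Assume 15 Group B subjects and one serious DRE judged expected and unrelated. The SAE outputs show 0/15, compatible with a true rate up to 21%. Counting the event gives 1/15, with an interval of 0.02 to 0.30.

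**Step 5: how likely this is.** The documents give no rate for such events. Under assumed per-subject rates of 1%, 2% and 5%, the chance of at least one in 15 subjects is 1 − (1 − p)^15 = 14%, 26% and 54%. These rates are assumptions to show the range; none comes from the documents.

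**The case against.** The strongest reply is that the note in 7.4.1.5 already deals with the cases that matter most. A patient with skin-only disease who develops organ involvement may well be judged worse than expected, and any suspicion of the product makes the event an SAE. This stands, and it confines the gap to serious events judged both expected and unrelated.

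Other points stand in part:
- **Indirect traces.** A withdrawal could show in Listing 3, a new medication in Listing 12 and abnormal laboratory values in Listings 23-26. A reader might infer that such an event would vanish from every output; the documents do not support that. But these traces would not identify the event as a serious systemic lupus event.
- **The AE route is ambiguous.** Section 12.3.1 also counts exacerbation of a pre-existing condition, and new conditions diagnosed after treatment, as AEs. A site might record the event as an AE as well. The SAE count would still miss it.
- **Safety Review Team monitoring.** The oversight is real, although Protocol 5.4.1 and 10.8 do not name DREs among the data reviewed (5.4.1 allows additional data). It is not a reported output.
- **The synopsis's general promise to list and summarise all data.** The SAP's numbered display list does not carry it through to DREs.

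A reader might also infer that the DRE rule does not fit the patients enrolled, because exclusion 6 removes "Subjects with active Systemic Lupus Erythematosus (SLE) and/or significant disease in any other organ than the skin". That goes too far. The criterion concerns active SLE and significant disease, as judged by the investigator, so a patient with quiescent SLE could enter and later flare. The SAP gap does not depend on this argument.

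Nor do the documents support calling the absence of a display for the SLE clinical assessment an error. Protocol 7.2 leaves that assessment to each site's usual practice and states no scale for it, and it is not an endpoint.

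**Conclusion.** The concern holds in a limited form. The protocol requires a DRE page that can hold events meeting the SAE definition, and the SAP has no output that reads it. A serious DRE judged expected and unrelated would be absent from Table 2.3 and from the SAE listings.

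The size is conditional. With 15 Group B subjects, one such event is the difference between 0/15 (upper limit 21%) and 1/15 (0.02 to 0.30). This assumes that an event occurs, that the investigator judges it expected and unrelated, and that the planned approximate number of 15 is reached. It is not a prediction, and nothing here shows that an event was missed. A reader might infer that following the plan necessarily gives a wrong safety summary; that is so only if such an event occurs.

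UV exposure adds little weight under this SAP: Section 2.1 records that no Group A subject was randomised, and Listing 15 already lists the AEs of PV failures. DREs in those subjects nevertheless have no listing either.

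**What to change.** Two additions to the SAP:

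1. A listing of all DREs for the Safety and PV Failures populations, with seriousness, expectedness and causality judgements where the CRF captures them. If there are none, an empty listing records that.
2. Alongside Table 2.3, the number of subjects with any SAE or any DRE meeting the SAE definition. Table 2.3 itself stays as it is.

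The expedited-reporting rule in Protocol 7.4.1.5 needs no change. No new procedure or visit is needed, since the protocol already requires the DRE page. The cost is SAP wording, one listing and one added count. The CRF is not among the documents, so whether the page records seriousness should be checked first. If it does not, seriousness would have to be assigned against the Appendix 3 definition, and that step documented, before database freeze. The small downside is that the reported serious-event count may be higher.
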